10.1.1 Definition of Baseline and change from baseline

Baseline for each parameter is defined as the last non-missing value measured prior to dosing, including repeat (vital signs andECGs and unscheduled (clinical laboratory parameters) readings (see [Section 10.1.2](#) for definitions of repeat and unscheduled readings).

Mean change from baseline is the mean of all individual subjects' change from baseline values. Each individual change from baseline will be calculated by subtracting the individual subject's baseline value from the value at the timepoint. The individual subject's change from baseline values will be used to calculate the mean change from baseline using a SAS procedure such as Proc Univariate.

10.1.2 Repeat and Unscheduled Readings

Repeat readings occur when the original vital signs or ECG result requires a recheck. Repeat readings are labelled as 'Repeat' in the listings. Prior to dosing, all readings taken in addition to the original reading are defined as predose repeats. Unscheduled post-dose repeat readings will not be used in the summarization and calculations."

With the exception of predose results described above, unscheduled readings for vital signs or ECGs are defined as readings collected >15 minutes from the actual time of the original reading. Unscheduled readings are labelled as 'Unscheduled' in the listings. Because unscheduled readings are not associated with any scheduled timepoint, they are excluded from all summaries (with the exception that they may be used as baseline, as stated in [Section 10.1.1](#)).

10.2 Demographics and Subject Disposition

The demographic variables age, sex, race, ethnicity, body weight, height, and BMI will be summarized and listed by hepatic function group. The CP score will be listed. Subject disposition will be summarized and listed by hepatic function group.

10.3 Pharmacokinetic Assessment

10.3.1 Pharmacokinetic Parameters

The following PK parameters will be determined where possible from the plasma concentrations of LOXO-292 using non-compartmental methods performed using Phoenix WinNonlin (Certara USA, Inc.) version 6.4 or higher:)

Parameter	Definition
C_{\max}	maximum observed concentration
t_{\max}	time to maximum observed concentration
AUC_{0-t}	area under the concentration-time curve (AUC) from Hour 0 to the last measurable concentration, calculated using the linear trapezoidal rule for increasing and decreasing concentrations
$AUC_{0-\infty}$	AUC extrapolated to infinity, calculated using the formula: $AUC_{0-\infty} = AUC_{0-t} + \frac{C_t}{\lambda_z}$ where C_t is the last measurable concentration and λ_z is the apparent terminal elimination rate constant
%AUC _{extrap}	percentage extrapolation for AUC
λ_z	apparent terminal elimination rate constant, where λ_z is the magnitude of the slope of the linear regression of the log concentration versus-time profile during the terminal phase
$t_{1/2}$	apparent terminal elimination half-life (whenever possible), where $t_{1/2} = \text{natural log } (\ln)(2)/\lambda_z$
CL/F	apparent systemic clearance
V_d/F	apparent volume of distribution during the terminal phase
MRT _{last}	mean residence time

Based on data from in vitro equilibrium dialysis study of a sample of pre-dose plasma from each subject, spiked with LOXO-292, the unbound fraction (fu) in plasma, expressed as a decimal, will be calculated from protein binding concentration data as the unbound drug concentration (concentration in buffer chamber) divided by the total drug concentration in plasma (concentration in the plasma chamber). The fu value determined for each subject will be used to calculate the following unbound LOXO 292 PK parameters for each individual subject:

$C_{\max,u}$ Unbound C_{\max} , calculated as $C_{\max} \cdot f_u$

AUC _{0-t,u}	Unbound AUC _{0-t} , calculated as AUC _{0-t} *f _u
AUC _{0-∞,u}	Unbound AUC _{0-∞} , calculated as AUC _{0-∞} *f _u
CL/F, _u	Unbound CL/F, calculated as Dose/AUC _{0-∞,u}
V _d /F, _u	Unbound V _d /F, calculated as CL/F, _u /λ _Z

Additional PK parameters may be determined where appropriate. The number of points used to estimate λ_Z, the lower and upper limits of the points used in estimation, and the adjusted coefficient for determination of exponential fit (R² adjusted) will be presented in a listing.

PK analysis will, where possible, be carried out using actual times recorded in the raw data . If actual times are missing, nominal times may be used with sponsor approval.

Concentrations are used as supplied by the analytical laboratory for PK analysis. The units of concentration and resulting PK parameters, with amount or concentration in the unit, will be presented as they are received from the analytical laboratory.

C_{max} and t_{max} will be obtained directly from the plasma concentration-time profiles. For multiple peaks, the highest postdose concentration will be reported as C_{max}. In the case that multiple peaks are of equal magnitude, the earliest t_{max} will be reported.

10.3.2 Criteria for Handling Plasma Concentrations Below the Limit (CBLL) of Quantification

Concentration values that are below the level of quantification (BLQ) will be set to zero, with defined exceptions as follows:

- Any embedded BLQ value (between 2 quantifiable concentrations) and BLQ values following the last quantifiable concentration in a profile will be set to missing for the purposes of PK analysis.
- If there are late positive concentration values following 2 BLQ concentration values in the apparent terminal phase, these values will be evaluated. If these values are considered to be anomalous, they will be set to missing.
- If an entire concentration-time profile is BLQ, the profile will be excluded from the PK analysis.

If a predose concentration is missing, these values are set to zero in PK analysis by default within Phoenix WinNonlin.

10.3.3 Criteria for the Calculation of an Apparent Terminal Elimination Half-Life Number of Data points

At least three data points will be included in the regression analysis and preferably should not include C_{max} .

Goodness of fit

When assessing terminal elimination phases, the R^2 adjusted value will be used as a measure of the goodness of fit of the data points to the determined line.

Regression-based parameters ($AUC_{0-\infty}$, λ_Z , $t_{1/2}$, CL/F , and $V_{d/F}$) will only be calculated if the R^2 adjusted value of the regression line is greater than or equal to 0.7

Period of Estimation

Time period used for the estimation of apparent terminal elimination half-lives, where possible, will be over at least two half-lives.

Where an elimination half-life is estimated over a time period of less than two half-lives, it will be flagged in the data listings at the discretion of the pharmacokineticist, and the robustness of the value should be discussed in the study report.

10.3.4 Calculation of AUC

- The minimum requirement for the calculation of AUC will be the inclusion of at least three consecutive plasma concentrations above the lower limit of quantification (LLOQ), with at least one of these concentrations following C_{max} .
- $AUC_{0-\infty}$ values where the percentage extrapolation is less than 20% will be reported. $AUC_{0-\infty}$ values where the percentage extrapolation is between 20 to 30% will be flagged and included in the descriptive statistics, whilst $AUC_{0-\infty}$ values where the percentage extrapolation is greater than 30% will be reported but excluded from descriptive statistics.

10.3.5 Anomalous Values

If a value is considered to be anomalous due to being inconsistent with the expected PK profile, it may be appropriate to exclude this point from the PK analysis. However, the exclusion of data must have strong justification and will be documented in the raw data and study report.

Embedded BLQ values may be considered anomalous depending on the route of administration and the characteristics of the drug.

- Positive predose value(s) greater than 5% of C_{max} may be excluded from the summary statistics of PK tables and statistical analysis at the discretion of the Pharmacokineticist.

10.3.6 Handling Rules for Missing or BLQ Values

For Pharmacokinetic Plasma Drug Concentration Data

The following rules will be applied if there are values that are BLQ or if there are missing values (eg, no result [NR]) in a plasma concentration data series to be summarized.

- For the calculation of summary statistics, BLQ values will be set to zero.
- If an embedded BLQ value is considered anomalous within the concentration-time profile, this value will be excluded from the summary statistics.
- Where there is NR, these will be set to missing.
- If there are fewer than three values in the data series, only the min, max and N will be presented. The other summary statistics will be denoted as not calculated (NC). BLQ is considered a value.
- If all the values are BLQ, then the arithmetic mean, arithmetic SD, median, min and max will be presented as zero, and the geometric mean and geometric CV% will be denoted as NC.
- If the value of the arithmetic mean or median is below the lower limit of quantification, these values will be presented as zero and the geometric mean and geometric CV% will be denoted as NC.

For Pharmacokinetic Parameters:

For the calculation of summary statistics of PK parameters, all NR and NC values in a data series will be set to missing.

The AUC values will be set to NC if they have been calculated using fewer than three concentrations, and/or three concentrations if the last is C_{max} .

10.4 Statistical Methods for Pharmacokinetic Data

10.4.1 Descriptive Statistics

Arithmetic means, %CV, SD, median, Min, Max, and n will be calculated for PK parameters separately in healthy subjects and subjects with hepatic impairment. Geometric mean and geometric %CV will be provided for all PK parameters except t_{max} . Median, min, max, and n will be calculated for t_{max} . In addition, summary statistics for protein binding will be tabulated by hepatic function group.

10.4.2 Primary Analysis

To evaluate the effect of hepatic function group on the PK of a single dose of LOXO-292, paired t-test will be performed for each hepatic impairment group versus the normal group with respect to 1 to 1 matching. The 1 to 1 matching comparisons of interests include:

- Subjects with severe hepatic impairment versus healthy matched control subjects.

- Subjects with moderate hepatic impairment versus healthy matched control subjects.
- Subjects with mild hepatic impairment versus healthy matched control subjects.

Since the comparison groups of subjects are independent in terms of degrees of hepatic impairment and dependent based on the matching criteria, paired Proc ttest in SAS will be used for this comparison on the natural log transformed PK parameters (AUC_{0-t}, AUC_{0-∞}, and C_{max}). The 90% confidence interval for the ratio between each level of impaired hepatic function versus the matched-control healthy subject group will be presented. The normality assumption will be explored to ensure no major deviation to the assumption exists. The corresponding results along with any outliers will be evaluated and can be included in the CSR appendix as needed. Any major outliers will be investigated case by case and determine the appropriate action on how to handle them.

Example SAS code:

```
proc ttest data= logpk alpha=0.1;  
by paramcd;  
paired normal*impairment;  
run;
```

where;

paramcd = categorical variable to indicate different PK parameters

impairment = natural log-transformed PK parameters for the subjects with hepatic impairment

normal = natural log-transformed PK parameters for the healthy matched controlled subjects

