**Statistical methods:**

**Pharmacokinetics:**

All subjects who have received a dose of LOXO-292, have at least 1 quantifiable plasma concentration, and for whom at least 1 PK parameter can be computed will be included in the PK Population. Plasma concentrations and PK parameters will be summarized by hepatic function

using descriptive statistics (number, arithmetic mean, standard deviation, coefficient of variation [CV%], geometric mean, geometric CV%, median, minimum, and maximum). In addition, summary statistics for protein binding will be tabulated by hepatic function group.

The primary analysis planned for this study is to evaluate the PK of LOXO-292 after a single dose in subjects with mild, moderate, or severe hepatic impairment, compared to subjects with normal hepatic function. The following statistical methodology will be used, based on 1 to 1 matching:

The 90% confidence interval of  $C_{max}$  and AUCs for the ratio between each level of impaired hepatic function versus the control group will be presented. Furthermore, if an individual healthy subject is matched to 1 subject from any or all hepatic impairment groups, then the primary PK parameters,  $C_{max}$  and AUCs, will be analyzed using the paired t-test to assess the difference between each impaired group and the healthy group. The p-value assessing the difference between each impaired group and the healthy group will be presented. For cases where 1 to 1 matching between the healthy and hepatic impaired groups are not achieved, an analysis of variance will be conducted. The specific procedures will be documented in the Statistical Analysis Plan.

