10.4.3 Analysis of Covariance

To evaluate the effect of hepatic function group on the PK of a single dose of LOXO-292In addition, an analysis of covariance (ANCOVA) will be performed on the natural log transformed AUC_{0-t}, AUC_{0-∞}, and C_{max}. The ANCOVA model will contain a categorical factor of population for subjects with various degrees of hepatic impairment (mild, moderate, and severe) and healthy matched control subjects, a categorical covariate (sex), and continuous covariates (age and BMI). The ratios of least square means (LSM) and 90% CI for the ratio of the PK parameter for each hepatic function group versus the matched normal group will be constructed using the exponentiation of the difference and the CIs from the ANCOVA analyses. These ratios will be expressed as a percentage relative to the healthy matched control cohort.

The 1 to 1 matching comparisons of interests include:

- Subjects with severe hepatic impairment versus healthy matched control subjects.
- Subjects with moderate hepatic impairment versus healthy matched control subjects.
- Subjects with mild hepatic impairment versus healthy matched control subjects.

Example SAS code:

```
proc mixed data = dataset;
class group sex;
model IPK = group sex age BMI / alpha=0.1 cl solution outpred=resids;
lsmeans group / pdiff alpha=0.1;
ods output lsmeans=lsmeans;
ods output diffs=diffs;
run;
quit;
```

Residual plots will be produced to assess the adequacy of the model.

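### SAP 10.4.2: the example code for the primary paired analysis gives healthy minus impaired, but the text promises the impaired/healthy ratio

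*SAP*

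**What the plan says.** SAP 10.4.2 lists three comparisons (severe, moderate and mild), each as impaired subjects against matched healthy controls. On the output it says: "The 90% confidence interval for the ratio between each level of impaired hepatic function versus the matched-control healthy subject group will be presented". The protocol synopsis, under Statistical methods, has the same direction for Cmax and "AUCs for the ratio between each level of impaired hepatic function versus the control group will be presented".

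The example SAS code in 10.4.2 runs PROC TTEST with alpha=0.1 by PK parameter, using the statement "paired normal*impairment". The key beneath it defines the two variables:

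- "normal = natural log-transformed PK parameters for the healthy matched controlled subjects"
- "impairment = natural log-transformed PK parameters for the subjects with hepatic impairment"

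Section 10.4.2 says nothing about changing the sign of the difference, swapping the limits or exponentiating. SAP 10.4.3 does cover back-transformation for the ANCOVA, where ratios and intervals "will be constructed using the exponentiation of the difference and the CIs from the ANCOVA analyses". It also fixes the reference group: "These ratios will be expressed as a percentage relative to the healthy matched control cohort".

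**The concern.** Within one section, the prose puts the healthy control in the denominator and the code puts the impaired subject there. The variable names leave no room for doubt, because the SAP defines them.

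The ratio of impaired to healthy exposure is the primary output of a study meant to inform dosing recommendations in hepatic impairment (protocol 1.4). Protocol 8.7 says the tables, figures and listings are programmed from the final SAP. If the code were run as printed, exponentiated, and put under the label the prose calls for, a rise in exposure would appear as a fall. The p-value would give no warning, because it is the same in either order.

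**Working it through.** The plan has no figure to reproduce here: the sample size rests on precedent, and no expected ratio or variability is given. The check therefore has two parts.

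**1. Direction**

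- Text (SAP 10.4.2, the protocol synopsis and SAP 10.4.3): impaired / healthy.
- Code: first-named minus second-named variable, that is, d = ln(healthy) − ln(impaired). That PAIRED A*B means A − B is standard SAS behaviour. The documents do not state it.
- The confidence level agrees: alpha=0.1 gives a two-sided 90% interval.

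If d has 90% limits (L, U), then exp(d) with limits (exp L, exp U) is healthy/impaired. The promised quantity is exp(−d), with limits (1/exp U, 1/exp L). The unreversed result is thus the exact reciprocal, with the limits inverted and swapped. The t statistic only changes sign, so the two-sided p-value is unaffected.

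**2. Size, by illustration**

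Inputs from the documents: 6 completers planned per group (SAP 8) and up to 8 enrolled per impairment group (SAP 6), taken as 6 or 8 pairs. Assumed: true impaired/healthy ratio 2.0, between-subject CV 30% to 50%, zero within-pair correlation.

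SD of the paired ln difference = √(2·ln(1 + CV²)):

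- CV 30%: √(2·ln 1.09) = 0.4152
- CV 50%: √(2·ln 1.25) = 0.6680

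Half-width = t(0.95, n−1)·SD/√n:

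- n = 6, t = 2.0150: 0.3415 (CV 30%) and 0.5496 (CV 50%)
- n = 8, t = 1.8946: 0.2781 (CV 30%) and 0.4475 (CV 50%)

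The promised interval is exp(ln 2 ± half-width). The unreversed interval is exp(−ln 2 ± half-width).

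| Pairs | CV | Promised impaired/healthy (90% CI) | Code output exponentiated, unreversed |
|---|---|---|---|
| 6 | 30% | 2.00 (1.42–2.81) | 0.50 (0.36–0.70) |
| 6 | 50% | 2.00 (1.15–3.46) | 0.50 (0.29–0.87) |
| 8 | 30% | 2.00 (1.51–2.64) | 0.50 (0.38–0.66) |
| 8 | 50% | 2.00 (1.28–3.13) | 0.50 (0.32–0.78) |

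As printed, the code stops at the log scale. With 6 pairs, ratio 2.0 and an assumed SD of the ln difference of 0.5, the half-width is 2.0150·0.5/√6 = 0.411. The estimate is −0.693 (−1.104 to −0.282), which is not a ratio. Exponentiated as it stands, it is 0.50 (0.33 to 0.75). Reversed first, it is 2.00 (1.33 to 3.02). The two-sided p-value is 0.019 both ways.

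**The case against.** The block is labelled as an example. It does not split by impairment group and does not back-transform, so it could not produce the reported table as it stands. The prose states the direction four times (three listed comparisons and the interval sentence), so no reader is left unsure of the intended ratio. Exponentiation is the only way from a mean log difference to a ratio, so that step is implied. The ANCOVA example code also names no control level and does not exponentiate; there too the prose does the work.

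The protocol ties the paired t-test to a p-value (synopsis), and protocol 8.5 takes the ratios and intervals from the ANCOVA.

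There are several safeguards. SAP 10.4.1 says "Geometric mean and geometric %CV will be provided for all PK parameters" (tmax excepted). An ANCOVA ratio near 200% would stand beside a paired ratio of 50%. Protocol 8.7 requires independent programmer review of all tables. The TFL shells, which are not available here, may already fix the labels.

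Most of this stands, and it keeps the point minor. It does not remove the point. This is the only code offered for the primary analysis, and it runs against the prose it illustrates. The SAP does attach a ratio interval to the paired analysis, and it states that it supersedes the protocol's statistical considerations (SAP 4). The implied exponentiation does not supply the missing sign reversal.

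**Conclusion.** The concern holds, as a minor correction. In SAP 10.4.2 the operand order in the code is opposite to the stated comparison, and the section states neither a reversal nor a back-transformation. The test, the log scale and the 90% level are not in question.

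If the reversal were carried through, each primary ratio would be its exact reciprocal, whatever the data. No data would be lost and the p-value would be unchanged. The illustrated intervals depend on the assumed ratio, CV and zero within-pair correlation; the reciprocal relation does not. The coded direction depends on standard SAS semantics. A reversal reaching the study report unnoticed is unlikely.

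**What to change.** In SAP 10.4.2, change the statement to `paired impairment*normal;`. Add one sentence: the mean log difference and its 90% limits are exponentiated to give the impaired/healthy geometric mean ratio and its 90% confidence interval.

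Optionally, as good practice and not because 10.4.3 is wrong, name the normal group as the control level for the LSMEANS differences in the ANCOVA code.

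The cost is one code line and one sentence before database lock, with no effect on data collection, subjects or design.

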10.4.3 Analysis of Covariance

To evaluate the effect of hepatic function group on the PK of a single dose of LOXO-292In addition, an analysis of covariance (ANCOVA) will be performed on the natural log transformed AUC_{0-t}, AUC_{0-∞}, and C_{max}. The ANCOVA model will contain a categorical factor of population for subjects with various degrees of hepatic impairment (mild, moderate, and severe) and healthy matched control subjects, a categorical covariate (sex), and continuous covariates (age and BMI). The ratios of least square means (LSM) and 90% CI for the ratio of the PK parameter for each hepatic function group versus the matched normal group will be constructed using the exponentiation of the difference and the CIs from the ANCOVA analyses. These ratios will be expressed as a percentage relative to the healthy matched control cohort.

The 1 to 1 matching comparisons of interests include:

- Subjects with severe hepatic impairment versus healthy matched control subjects.
- Subjects with moderate hepatic impairment versus healthy matched control subjects.
- Subjects with mild hepatic impairment versus healthy matched control subjects.

Example SAS code:

```
proc mixed data = dataset;
class group sex;
model IPK = group sex age BMI / alpha=0.1 cl solution outpred=resids;
lsmeans group / pdiff alpha=0.1;
ods output lsmeans=lsmeans;
ods output diffs=diffs;
run;
quit;
```

Residual plots will be produced to assess the adequacy of the model.

10.5 Safety and Tolerability Assessments

10.5.1 Adverse Events

All safety data will be listed by subject. All AEs occurring during this clinical trial will be coded using the Medical Dictionary for Regulatory Activities (MedDRA®), Version 21.0. A baseline sign and symptom is defined as an AE that starts after the subject has provided written informed consent and that resolves prior to the receipt of first dose of study drug, or an AE that starts prior to the first dosing occasion and does not increase in severity after dosing. A treatment-emergent AE (TEAE) is defined as an AE that occurs postdose or that is present predose and becomes more severe postdose. The severity of AEs will be categorized based on the National Cancer Institute Common Terminology Criteria for Adverse Events (CTCAE) Version 5.0. The Investigator (or designee) will make a determination of the relationship of the AE to the study drug using a 2-category system (i.e. Not Related or Related). Onset times postdose are calculated from the last dose administered. The AE severity and relationship are determined by the investigator at the site.

All AEs captured in the database will be listed in by-subject data listings including verbatim term, coded term, part, severity grade, relationship to study treatment, outcome, and action. TEAEs, drug-related TEAEs, and TEAEs by severity will be summarized by each hepatic function group. The frequency of TEAEs (the number of TEAEs, the number of subjects experiencing a TEAE, and the percentage of subjects experiencing a TEAE) will be summarized by each hepatic function group, and Medical Dictionary for Regulatory Activities (MedDRA) System Organ Class (SOC) and Preferred Term (PT). The summary and frequency TEAE tables will be presented for all causalities and for those TEAEs considered related to the study drug (those that have a relationship of 'RELATED'). Any severe TEAEs, serious TEAEs (SAEs), or TEAEs leading to discontinuations will be tabulated. For any AEs that change severity ratings the AE will be included only once under the maximum severity rating in the summaries.

